15.3 Secondary analysis

The secondary outcomes measures will be:

- duration of survival;
- mortality at 28 days;
- mortality at discharge from critical care and discharge from hospital;
- mortality at one year;
- SOFA score at 6 hours and 72 hours (adjusted for baseline);
- requirement for, and duration of, monitoring and support of specific organ systems (CCMDS);
- duration of ED, critical care unit and acute hospital stay;
- health-related quality of life (EQ-5D) at 90 days and one year;
- resource use and costs at 90 days and one year;
- lifetime incremental cost-effectiveness.

Secondary analyses of binary outcomes (mortality, requirement for organ support) will be performed by Fisher's exact test and, where appropriate, adjusted logistic regression. Secondary analyses of continuous outcomes (SOFA score, duration of organ support, duration of ED, critical care and acute hospital stay, health-related quality of life) will be performed by t-tests or ANCOVA (for outcomes measured at baseline) or by nonparametric or bootstrapped alternatives (depending on the distribution of the outcome variable) and, where appropriate, adjusted linear regression. Comparisons of duration of organ support will be performed using the days alive and free of organ support up to 28 days. Duration of ED, critical care unit and acute hospital stay will be compared overall and for survivors and non-survivors separately. Secondary analyses of time-to-event data (duration of survival) will be performed by Kaplan-Meier methods and Cox proportional hazards modelling.

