8.1 Follow-up after initial hospital discharge

All patients surviving to discharge from an acute hospital will be checked against death registrations on the NHS Central Register (NHSCR) for subsequent reporting of mortality data. This will be achieved through regular application of the 'list cleaning' service offered by the Medical Research Information Service (MRIS).

Following randomisation into the trial, the ICNARC CTU will write to each patient's General Practitioner to inform them of the patient's participation in the trial, including a brief description of the trial and a request that the General Practitioner notifies the ICNARC CTU of any events of note.

Patients recorded on the NHSCR as being alive at 90 days and at one year post-randomisation will receive questionnaires to record their health-related quality of life, subsequent hospital admissions and use of personal health services. Questionnaires will be sent with a personally signed letter, a pen enclosed, and a stamped addressed envelope.¹⁸

Health-related quality of life will be measured by the EuroQol (EQ-5D) measure (see: Appendix 3). ¹⁹ EQ-5D is a widely-used generic quality of life measure that can be combined with survival data to calculate Quality-Adjusted Life Years (QALYs). Information on subsequent hospital admissions and the use of personal health services will be recorded on separate healthcare resource use questionnaires. ²⁰

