For each patient, the number of days in critical care will be recorded and assigned to a Healthcare Resource Group (HRG) using mandated data collected for the Critical Care Minimum Data Set (CCMDS). The HRG categorisation will recognise the use of high cost interventions for septic shock (e.g. recombinant human activated protein C). These activity data will be combined with unit cost per hospital bed-day (by HRG) from the NHS Payment by Results database.

Readmissions will be recorded on the trial database. The use of personal health services will be recorded by patient questionnaire at one year, and valued using unit costs taken from published sources.³⁰ Data from the EQ-5D questionnaires at one year will be combined with survival data to report quality-adjusted life years (QALYs).

The CEA will report the mean (95% confidence interval) incremental costs and QALYs at one year, using the same comparators as the main statistical analysis (see above).

The CEA will use a decision-model to project lifetime cost-effectiveness. The model will use a similar structure to previous CEA of protocolised care in US critical care units³¹ and of interventions for severe sepsis in the UK.³² The model will use the best, most relevant input parameters for this particular NHS context. Survival analysis of the RCT data will provide a basis for extrapolating any within trial differences in costs and QALYs.³³ The model will also use external data on the long-term survival for patients following septic shock.³⁴ The sensitivity analysis will test whether the results are robust to methodological assumptions, for example: the specification of the statistical model and data source (RCT versus external data) used to extrapolate the RCT results, and the source of unit cost data (average unit costs from Payment by Results versus Trust-specific estimates).

The CEA will therefore provide a thorough assessment of whether early, goal-directed, protocolised resuscitation is cost-effective for emerging septic shock.

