15.7 Sample size calculation

Estimates for baseline mortality in the usual resuscitation arm have been based on the CMPD. Patients were identified if they were admitted to a critical care unit from the ED having previously been not in hospital and if they satisfied at least two SIRS criteria and had evidence of infection. These definitions are relaxed from the entry criteria to the trial as patients are likely to have had physiological abnormalities stabilised prior to admission to critical care. During 2005 and 2006, 24,155 patients were admitted to 156 participating critical care units

ProMISe v2.3 31/08/2012

from the ED (24 admissions per unit per year). Of these, 6,671 (28%) met the above criteria. Hospital mortality for these patients was 35%. Long-term follow-up studies of patients with severe sepsis indicate that, of patients discharged home from hospital, a further 16% will have died by 90 days.³⁵ However, these studies were predominantly based in the US, where the high provision of chronic care facilities means that more deaths occur outside hospital. We have therefore based our sample size calculations on an anticipated 90-day mortality in the usual resuscitation arm of 40%.

Rivers *et al* reported an absolute risk reduction of 16% in hospital mortality (13% at 60 days);⁴ however, as this was a single-centre trial with concerns over internal and external validity, it is essential that ProMISe is powered to detect a smaller difference.

To achieve 80% power to detect a reduction in 90-day mortality from 40% to 32% associated with early, goal-directed, protocolised resuscitation versus usual resuscitation (P<0.05) requires a sample size of 589 patients per arm (1178 total). Allowing for 6% of patients refusing consent to follow-up (in the similar PAC-Man trial, only 2% of patients refused consent following randomisation) or being lost to follow-up prior to 90 days, we will aim to recruit 630 patients per arm (1260 total). This sample size will give in excess of 99% power to detect an absolute risk reduction of the magnitude observed in the Rivers *et al* trial. In the event that the mortality in the control arm is lower than anticipated, the trial would have greater power to detect the same absolute risk reduction. If the mortality were as low as 25%, the trial would have >80% power to detect a reduction to 18%.

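### Length of stay is compared within survivors and non-survivors, which is not a randomised comparison, and the overall comparison measures bed-days rather than clinical benefit

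*Protocol*

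**What the plan says.** Section 15.3 of the protocol lists duration of emergency department (ED), critical care and acute hospital stay among the secondary outcomes and states: "Duration of ED, critical care unit and acute hospital stay will be compared overall and for survivors and non-survivors separately". Stay is grouped there with the other continuous outcomes, whose analyses "will be performed by t-tests or ANCOVA (for outcomes measured at baseline) or by nonparametric or bootstrapped alternatives (depending on the distribution of the outcome", with adjusted linear regression where appropriate. None of these methods deals with death.

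The sentence just before the one on stay treats organ support differently: "Comparisons of duration of organ support will be performed using the days alive and free of organ support up to 28 days". Death is therefore built into one duration outcome and not into the next.

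EQ-5D is analysed as a continuous outcome in the same section. Section 8.1 determines who can supply it: "Patients recorded on the NHSCR as being alive at 90 days and at one year post-randomisation will receive questionnaires". Survival and EQ-5D are joined only in the QALY (section 15.5).

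Section 2.2.2 gives the objective for stay as a comparison, without a direction. Section 15.5 mentions a reduction in stay as a possible cost saving, and section 2.1.2 reports that the earlier single-centre trial shortened hospital stay for survivors. Section 15.2 applies the intention-to-treat principle to all analyses.

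**The concern.** Survival is the clinical primary outcome, and the trial is built on the hypothesis that treatment changes it. Once patients are sorted by whether they survived, the two groups of survivors are no longer the groups that randomisation produced, and the same is true of the non-survivors. A difference in stay within either stratum can come from who is in it, with no effect on anyone's stay.

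The overall comparison keeps everyone and is sound as a measure of beds used. Its weakness is interpretation: a patient who dies on the first day has the shortest stay. If shorter is read as better, a treatment that prevents early deaths is marked down for it.

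At stake is the interpretation of secondary outcomes that readers will set beside the earlier trial's shorter stay. No primary result is involved.

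**Working it through.** **Inputs from the protocol.** 90-day mortality 40% v 32% and 589 per arm before loss (section 15.7). Mean stay of 9 + 14 = 23 days for severe sepsis admitted to critical care through the ED (section 2.1.1). The protocol gives no stay by survival status, so every such figure below is an assumption.

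**The plan's own figure.** For 40% v 32%, 80% power and two-sided 5% (sidedness assumed), the two-proportion formula gives 564 per arm, and 589 with continuity correction. This matches section 15.7, and 589 is used below.

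**Who is in each stratum.** If nobody is harmed, 60% survive in either arm, 8% survive only if treated, and 32% die in either arm.
- Intervention survivors with no control counterpart: 8/68 = 11.8%.
- Control non-survivors with no intervention counterpart: 8/40 = 20%.

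**Direction of the overall comparison.** With no other effect on stay, and saved patients staying as long as other survivors (mean S, against D for non-survivors), the difference in overall mean stay is 0.08 × (S − D). Fixing the control mean at 23 days gives S = (23 − 0.4D)/0.6.
- D = 3: S = 36.3, difference +2.7 days.
- D = 8: S = 33.0, difference +2.0 days.
- D = 20: S = 25.0, difference +0.4 days.
- D = 23: S = 23.0, difference 0.
- D = 30: S = 18.3, difference −0.9 days.

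The better-surviving arm has the longer stay whenever D is below S.

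**Size against sampling error.** Assume log-normal stays with medians of 5 days for deaths, 14 for survivors, and 14 or 28 for the saved 8%, with a common log-SD s. The mean is median × exp(s²/2), and the mean square is median² × exp(2s²).

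For s = 0.8 and saved patients at 28 days:
- Control mean: (0.40×5 + 0.60×14) × 1.377 = 10.40 × 1.377 = 14.3.
- Intervention mean: (0.32×5 + 0.60×14 + 0.08×28) × 1.377 = 12.24 × 1.377 = 16.9.
- Variances: 253.8 and 393.2. SE = √((253.8 + 393.2)/589) = 1.05.
- z = 2.53/1.05 = 2.4 for a longer stay.
- Survivors only: 19.3 v 21.5 days, z = 1.5.

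For days alive and out of hospital to day 90, each death scores 0 (all deaths taken as in hospital) and each survivor scores 90 minus the stay, capped at 90. Here that gives 42.6 v 47.0.

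| Saved patients' median | s | Overall mean stay, control v intervention | z | Survivors' mean stay | z | Gain in days alive and out of hospital |
|---|---|---|---|---|---|---|
| 14 d | 0.6 | 12.5 v 13.3 | 1.4 | no difference | 0 | 5.9 |
| 14 d | 1.2 | 21.4 v 22.8 | 0.6 | no difference | 0 | 5.3 |
| 28 d | 0.6 | 12.5 v 14.7 | 3.2 | 16.8 v 18.7 | 2.2 | 4.6 |
| 28 d | 0.8 | 14.3 v 16.9 | 2.4 | 19.3 v 21.5 | 1.5 | 4.4 |
| 28 d | 1.2 | 21.4 v 25.1 | 1.4 | 28.8 v 32.1 | 0.8 | 4.1 |

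**EQ-5D.** Assume 0.65 for those who survive in either arm and 0.30 to 0.50 for the saved. Among survivors the difference is (0.60×0.65 + 0.08×0.30)/0.68 − 0.65 = −0.04, or −0.02 with 0.50. With deaths counted as 0 it is 0.08×0.30 = +0.02 to 0.08×0.50 = +0.04.

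**The case against.** **Overall stay is a legitimate comparison.** It includes every randomised patient, and the costing needs bed-days. If saved patients occupy more beds, a longer stay is a true finding. A reader might infer that the planned test makes a life-saving treatment look harmful. That happens only if stay is read alone and shorter is taken as better; the objective asks only for a comparison, and mortality is the primary outcome. This stands, which is why overall stay should be kept.

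**The survivor split has a purpose.** It allows comparison with the earlier trial's result in survivors. That justifies showing it, but not testing it as a treatment effect.

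**EQ-5D is partly covered.** Incremental cost per QALY at one year is a primary endpoint, and the QALY includes survival. What remains is a matter of labelling.

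**SOFA.** A reader might infer that deaths before 72 hours simply drop out of "SOFA score at 6 hours and 72 hours (adjusted for baseline"). The protocol is silent on this, the rule belongs in a statistical analysis plan not seen here, and the analysis is baseline-adjusted with nonparametric options. The document does not support a finding on SOFA.

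**The size rests on chosen inputs.** This also stands. If saved patients stay like other survivors, overall z is only 0.6 to 1.4 and the survivor difference is nil. The setting closest to the 23-day mean in section 2.1.1 (s = 1.2, control mean 21.4) gives z = 1.4 even with saved patients at 28 days. The 12% assumes the full hypothesised effect and no harm to anyone.

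**Conclusion.** The point holds for length of stay. The survivor and non-survivor comparisons are not randomised comparisons if treatment affects mortality, whatever the stay distributions. The overall comparison is valid for bed-days but not as evidence of clinical benefit.

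The direction of the overall difference depends on non-survivors staying less time than survivors, and its size depends on how long saved patients stay. The protocol reports neither. Within the assumed range the z value runs from 0.6 to 3.2 towards a longer stay, while days alive and out of hospital favour treatment by 4.1 to 5.9 days. These figures illustrate the problem and do not predict the trial's results. The effect should be small for ED stay.

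EQ-5D needs only a label and reading alongside the QALY.

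**What to change.** In section 15.3, or in the analysis plan before unblinding:

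1. For critical care and hospital stay, make days alive and out of critical care and out of hospital to a fixed day the tested clinical outcomes. Time to discharge alive with death as a competing event is an alternative. Either would match the organ-support measure in the same section. State whether readmissions count.
2. Keep overall stay, including ED stay, as a resource-use measure for the economic evaluation.
3. Report stay by survival status descriptively, without P values.
4. Label the EQ-5D comparison as one among survivors and interpret it with the QALY.

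The cost is wording. Section 8.0 already lists discharge and location-change dates and survival status, so a measure confined to the index admission needs no new data. One small downside is that the composite mixes survival with duration, so mortality and stay must be shown beside it.

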15.4 Subgroup analysis

Subgroup analyses will be performed to test for interactions between the effect of each trial arm and baseline covariates. An important *a priori* subgroup analysis will test whether the effect of early, goal-directed, protocolised resuscitation differs according to the degree of protocolisation of care delivered within usual resuscitation. This will be assessed in each site from the data collected on usual resuscitation patients. In addition, the following covariates will be tested:

- age;
- severity of illness MEDS score;²⁶
- severity of organ failure SOFA score;²¹
- time from ED presentation to randomisation.

Subgroup analyses of a trial adequately powered on a primary endpoint will inevitably be underpowered, and a non-significant interaction test will not rule out the possibility that a subgroup effect exists. Based on simulation studies, a subgroup analysis of this trial is likely to have around 30% power to detect a subgroup effect of equivalent magnitude to the overall anticipated treatment effect and 80% power to detect a subgroup effect of twice this magnitude. To Combining the data from ProMISe with those from the ongoing ProCESS and ARISE RCTs in the US and Australia in an individual patient data meta-analysis will allow greatly increased power for investigation of interaction effects.

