2.1.3 Early, goal-directed, protocolised resuscitation for emerging septic shock in the UK

The plausible biological rationale for early, goal-directed, protocolised resuscitation, combined with the results of the single-centre, US trial and some observational studies, has led to its recommendation for initial management of all patients with severe sepsis in the internationally, professionally-endorsed Surviving Sepsis Campaign's (SSC) Guidelines for resuscitation and management of severe sepsis. 9;10 However, adoption and compliance with these SSC resuscitation and management bundles remains limited.

Current resuscitation practice in the UK, though not standardised across hospitals, usually involves intravenous fluid and vasoactive drug administration with the intensity of resuscitation typically being determined by clinical assessment. Therapeutic strategies to improve ScvO₂ are not routinely employed during resuscitation in UK hospitals.

Several surveys and studies have reported barriers to the implementation of early, goal-directed, protocolised resuscitation for emerging septic shock. These include: recognition of patients; time required to deliver the protocol; local staffing and functioning of the ED; available resources; concerns about the invasiveness/aggressiveness; requirement for collaboration across specialities (emergency medicine, acute medicine and critical care medicine); and equipoise over the current evidence. A recent survey of 173 English EDs (2007) indicated that only 19% perform some form of early, goal-directed, protocolised resuscitation but that a further 10% were in some phase of planning this.¹¹ Only two publications have evaluated the SSC resuscitation bundle in a UK setting - one, an audit of a hospital implementing the SSC resuscitation bundle and the other, a non-randomised trial in two NHS acute hospitals. These demonstrated an association between compliance with the SSC resuscitation bundle, or a modified version (without invasive monitoring), and reduced mortality in a predominantly ward based patient population¹².

Reports of successful implementation of early, goal-directed, protocolised resuscitation have identified important enablers including: leadership (local champion); communication, education and training; buy-in to the protocol; provision for protocol transition from ED to the critical care unit; and locally determined delivery.

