2.2 ProMISe

The aim of ProMISe is to compare early, goal-directed, protocolised resuscitation for patients presenting with early signs of severe sepsis/septic shock. The trial design is an open, multicentre, parallel group RCT.

Patients are randomised between early, goal-directed, protocolised resuscitation and usual resuscitation. The intervention arm is delivery of the early, goal-directed, resuscitation protocol (with pre-determined haemodynamic goals). The control arm is delivery of usual resuscitation i.e the care the patient would usually receive if they were not recruited into ProMISe.

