3.2 Site initiation and activation

3.2.1 Inclusion criteria at the site level

The following criteria must be met for a site to participate in ProMISe – a site must:

- identify and sign-up local investigators ("champions") from, at least, emergency medicine and critical care medicine;
- not be providing early, goal-directed, protocolised resuscitation as part of standard resuscitation practice;
- identify a dedicated ProMISe Research Nurse (to be funded, or part-funded, centrally);
- agree to incorporate ProMISe into routine ED activity particularly highlighting the importance of screening at ED presentation;
- agree to adhere to randomisation and to ensure compliance;
- agree, where possible, to recruit all eligible patients to ProMISe and to maintain a ProMISe Screening Log to include reasons why eligible patients were screened and not recruited;

All screened and eligible patients will be recorded to establish an unbiased case selection and full reporting according to the CONSORT statement.²⁴

On agreement to participate, and having met all site level inclusion criteria, a ProMISe Research Nurse should be identified and seconded. Unless ScvO₂ measurement is consistently part of a site's standard resuscitation, the site will be eliqible to participate in ProMISe.

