7.1.2 Usual resuscitation

For patients randomised to usual resuscitation, all investigations, monitoring and treatment will be instituted, as considered appropriate, by the treating clinician(s). For these patients, the ProMISe early, goal-directed, resuscitation protocol and associated intervention arm equipment will not be provided. As soon as practicable, and according to local practice, patients should be admitted for in-patient care and transferred to an appropriate hospital location.

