16.5 Contamination

A theoretical concern in an open trial is that the usual resuscitation arm could gradually incorporate elements of the protocol, thereby affecting the capacity to detect the treatment effect. Contamination will be minimised by:

- the small number of patients recruited from each site;
- frequent ED staff rotation and multiple shifts;
- training, providing the protocol to, and delivering early, goal-directed, protocolised resuscitation by, a locally-determined ProMISe Team;
- delivering usual resuscitation from routine ED staff.

One possible strategy to reduce contamination would be to use a cluster-randomised design. However, heterogeneity, both in terms of standard practice and outcomes, is high and consequently the sample size for a cluster-randomised trial would need to be extremely large to be able to detect the same benefit. Analysis of patients in the CMPD admitted to critical care units from the ED with severe sepsis gives an intraclass correlation coefficient for the between site variation in mortality of 0.04. In the context of this trial, this would translate to a design effect of approximately 2, meaning that around 100 hospitals would need to participate in order to complete the trial in the proposed time frame. We therefore concluded that a cluster-randomised trial would not be feasible. This conclusion is backed up by the experience of a previous large, cluster-randomised trial of a complex critical care intervention delivered outside the critical care unit – the MERIT trial. Despite recruiting over 100,000 patients from 23 hospitals, the between-cluster variation within this trial was higher than anticipated, rendering it underpowered and ultimately inconclusive. In addition to this, outcomes improved over time in the control hospitals suggesting that the cluster-randomised design may not have been effective in reducing contamination.

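### The a priori subgroup on protocolisation of usual care labels each site from its own control patients' post-randomisation care, so a spurious interaction can arise if that care tracks severity

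*Protocol*

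**What the plan says.** Protocol section 15.4 states that the subgroup analyses will "test for interactions between the effect of each trial arm and baseline covariates". The first factor it names, and the only one it calls important, is whether the effect "differs according to the degree of protocolisation of care delivered within usual resuscitation". It then fixes where that information comes from: "This will be assessed in each site from the data collected on usual resuscitation patients". The other factors are age, MEDS, SOFA and time from ED presentation to randomisation, all known at or before randomisation.

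Other sections bear on this:

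- Section 2.2 makes usual resuscitation a randomised arm: "Patients are randomised between early, goal-directed, protocolised resuscitation and usual resuscitation".
- Section 7.1.2 leaves control-arm investigation, monitoring and treatment to the treating clinician.
- Section 2.1.3 describes current UK practice "with the intensity of resuscitation typically being determined by clinical assessment".
- Section 16.5 accepts that "the usual resuscitation arm could gradually incorporate elements of the protocol".
- Section 3.2.1 requires that a site "not be providing early, goal-directed, protocolised resuscitation as part of standard resuscitation practice". This is a check on usual practice made before a site opens.

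The protocol does not define the protocolisation score. That can properly be left to the SAP. The data source, however, is stated in the protocol.

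**The concern.** A subgroup factor should not be able to move with the outcome of one arm only. Here it can. The label is measured after randomisation, in controls alone, and those controls are also the comparison group for the treatment effect at their site.

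Suppose sicker patients receive more lines, monitoring and vasoactive drugs. A site whose few controls happen to be sicker then scores as more protocolised and also has more control deaths. Its intervention patients, randomised separately, are no sicker. The treatment effect looks larger at that site for reasons unrelated to its practice.

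At stake is the reading of one named a priori interaction: whether the effect depends on how protocolised existing care is. Section 15.4 also plans an individual patient data meta-analysis with two other trials to study interactions. Pooling shrinks random error but not this bias, so the problem would carry over if the same classification were used there.

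**Working it through.** **1. The protocol's own figures reproduce.** For 40% versus 32%, two-sided 5% and 80% power, the sample size is 564 per arm without and 589 with continuity correction; section 15.7 states 589. Allowing for 6% loss, 1178/0.94 = 1253.2, or 1254, against 1260 stated. For two equal subgroups the standard error of the interaction is twice that of the main effect, so power is Φ(m(1.96 + 0.84)/2 − 1.96). This gives 28.8% for m = 1 and 80.0% for m = 2, against about 30% and 80% in section 15.4. None of these figures is in dispute.

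**2. Inputs from the protocol.** Target 1260 (630 per arm) and a minimum of 48 sites: 630/48 = 13.1 controls per site. Control mortality 40%. Between-site ICC for mortality 0.04 (section 16.5), which is a logit SD of √(0.04/0.96 × 3.29) = 0.37.

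**3. Assumptions not in the protocol.** Log-odds of death 1.0 per SD of severity. Within-site correlation ρ between care score and severity, from −0.4 to 0.6. Between-site share of care-score variance (care ICC), from 0.05 to 0.6. Sites split at the median score.

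**4. Closed-form size.** With n controls per site, the site score has variance V = ICC + (1 − ICC)/n, and its covariance with the controls' mean severity is C = ρ√(1 − ICC)/n. After a median split the two halves differ in mean control severity by 2√(2/π) × C/√V = 1.596 C/√V. Multiplying by the average p(1 − p), which is 0.195 under these assumptions, gives the approximate shift in control mortality.

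For n = 13, ρ = 0.6:

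- ICC 0.05: V = 0.123, C = 0.0450, severity difference 0.205 SD, shift 4.0 points.
- ICC 0.3: V = 0.354, C = 0.0386, difference 0.104 SD, shift 2.0 points.
- ICC 0.6: V = 0.631, C = 0.0292, difference 0.059 SD, shift 1.1 points.

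**5. Simulation with no treatment effect and no interaction.** 48 sites, 13 patients per arm per site, Wald test of the log-odds-ratio interaction, 3,000 runs per cell. Entries are the spurious difference in risk difference, high minus low protocolisation (negative means the intervention looks better at high sites), with type I error in brackets.

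| ρ | care ICC 0.05 | care ICC 0.3 | care ICC 0.6 |
|---|---|---|---|
| 0 | 0.0 (4.6%) | −0.1 (4.5%) | −0.1 (5.4%) |
| 0.2 | −1.3 (5.9%) | −0.7 (5.1%) | −0.2 (4.2%) |
| 0.4 | −2.6 (7.3%) | −1.4 (4.5%) | −0.6 (4.5%) |
| 0.6 | −3.8 (10.0%) | −2.0 (6.7%) | −1.2 (5.6%) |
| −0.4 | +2.7 (7.8%) | +1.4 (5.3%) | +0.5 (5.1%) |

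The simulation error on a 5% rate is √(0.05 × 0.95/3000) = 0.4 points, so entries between about 4% and 6% cannot be told from nominal. The sizes agree with step 4. A separate simulation gave −1.4 to −2.7 points at ρ = 0.4 and −1.8 to −4.1 at ρ = 0.6.

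**6. Sensitivity (2,000 runs per cell).** With 6 controls per site (104 sites) and ρ = 0.6: −6.8 points (21.5%) at care ICC 0.05 and −4.1 (10.0%) at 0.3. With severity log-odds 1.5, 13 controls and ρ = 0.6: −5.2 (15.3%) and −2.5 (7.0%). A real common treatment effect changes little: −3.8 (9.0%) and −1.8 (5.7%) at ρ = 0.6.

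**7. Remedies.** Classifying sites from 13 usual-care patients outside the comparison (ρ = 0.6) gave −0.01 and +0.09 points, with type I error 4.4% and 5.5%, at care ICC 0.05 and 0.3. In the worst cell of step 5, adjusting the interaction model for baseline severity moved the spurious log-odds ratio from −0.16 to 0.00 and type I error from 10.7% to 4.1% (1,500 runs). With severity measured at reliability 0.6 the figures were −0.08 and 6.6%. In a separate simulation with reliability 0.7, adjustment removed about two thirds or more of the artefact, with type I error 3% to 6%.

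**The case against.** A reader might infer that a false interaction is built into the design and always favours the more protocolised sites. The documents do not support that. There is no bias if the score is unrelated to prognosis within site, and a negative correlation reverses the sign.

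Protocolisation is also not the same as intensity. A score of pathway features, such as lactate taken or goals recorded, need not rise with severity, and the score is for the SAP to define. This stands in part. But the resuscitation data listed in section 8.0 are line insertion, hourly physiological goals, and interventions by amount and type, and a score built from them is likely to follow severity to some degree. The SAP can choose the score, but to change the data source it would have to depart from the protocol.

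Section 16.5 says that heterogeneity in standard practice is high, which is where the artefact is small: 0.6 to 2.0 points at care ICC 0.3 to 0.6 and ρ 0.4 to 0.6. That is fair, although section 3.2.1 narrows the range by excluding sites that already provide the protocol.

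A self-reported site form would record stated practice rather than care delivered, and would miss drift. This also stands, and is why such a form belongs in a sensitivity analysis. Finally, this is one interaction test in a set that section 15.4 itself calls underpowered.

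**Conclusion.** The point holds in conditional form. The protocol places a post-randomisation, control-arm-only measure among baseline covariates and fixes a data source that can bias the interaction.

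At the planned 13 controls per site the artefact is about 0 to 4 percentage points with type I error about 4% to 10%, for ρ between 0 and 0.6 and a severity log-odds of 1.0. The upper end is about half the 8-point design effect (40% − 32%). It exceeds this range at small sites or with a stronger severity effect, and shrinks towards nothing where real practice differences are large. Neither ρ, the care ICC nor the severity effect is given in the protocol, so neither the size nor the direction can be settled from it.

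The primary analysis, the sample size and the stated interaction power are unaffected. This is worth correcting, chiefly because the correction is cheap.

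**What to change.** - In section 15.4, stop describing this factor as a baseline covariate; say that it is a site-level measure taken after randomisation in the control arm.
- Fit its interaction model with adjustment for baseline severity. MEDS and SOFA are already named in section 15.4, and baseline severity is already collected (sections 8.0 and 9.0).
- Build the site score from control-arm care adjusted for the control patients' baseline severity. This step was not simulated by itself.
- As a sensitivity analysis, classify sites on usual practice recorded at the site-level eligibility check in section 3.2.1, frozen before unblinding.

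The cost is some SAP wording and one short record per site. The downside is small: that record is self-reported, is retrospective for sites already open, and does not capture drift in delivered care.
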